#### **6.3** Follow-Up Procedures

Subsequent to Cycle 1 Day 1, patients will be followed clinically, radiographically, and with bloodwork. A detailed medical and physical examination will be performed at 8 weeks and 16 weeks, 6 months, 12 months, 18 months and 24 months. A complete blood count (CBC) and comprehensive chemistry panel and CT scan including the treated site will be performed at the 8 week and 16 week follow-up and will continue at intervals of every 6 months until 2 years post SBRT treatment.

Tumor measurements (Recist 1.1) at 8 weeks (+/- 10 days) and 16 weeks (+/- 10 days) will be used to determine radiographic response.

#### 6.4 Duration of Therapy

The patient will receive CBI as indicated and recommended by the treating medical oncologist.

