CBI PRODUCT DOSAGE AND ADMINISTRATION	Commercially available checkpoint blockade immunotherapy will be administered intravenously as clinically indicated.
CONTROL GROUP	CBI Alone
PROCEDURES	1. Physical exam 2. Three Research Blood draws 3. CT or MRI of Involved Site 4. PET-CT (optional) 5. SBRT 6. IV CBI administration

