#### **6.2** Therapeutic Procedures

Patients will be pre-screened for eligibility and should be enrolled and randomized prior to starting immunotherapy. However, patients who have started immunotherapy up to 5 days prior to enrollment will be still be eligible for screening, randomization, and enrollment.

Upon confirmation of eligibility and enrollment in the study, the following will be completed:

- 1) Demographics review, medical history and clinical exam
- 2) Review of concurrent medications
- 3) Vital signs, height and weight
- 4) Laboratory Bloodwork including: CBC, BMP, LFT.
- 5) Plasma and Peripheral blood mononuclear cells will be collected and subsequently frozen for immune monitoring assays.
- 6) Tumor measurements (Recist 1.1) within 4 weeks prior to start of CBI

Upon randomization into the SBRT arm of the protocol, patients will be seen by at least one of the Co-Investigator Radiation Oncologists. CT simulation will be performed with fabrication of a radiation therapy immobilization device (such as a Vac-Lok) which will be custom made for each patient. The treating radiation

oncologist will identify the location of the tumor. Gross tumor volume (GTV) delineation will be performed on sequential axial computed tomography images. An SBRT treatment plan will be developed based on tumor size and location. The dose will be prescribed to the minimal isodose line that completely covers the GTV plus a 5 mm margin. Adjacent normal structures including but not limited to the chest wall, spinal cord, heart, esophagus, aorta, kidneys, rectum, bowel, liver, and stomach within 5 cm of the GTV will be identified for the purpose of limiting incidental radiation to these structures.

In addition, prior to treatment delivery, a four-dimensional cone beam CT study will be performed on individual patients to assess respiration in these patients and to determine tumor targeting accuracy for those tumors that may be subject to respiratory motion such as those in the lung, abdomen, or liver. If tumor motion is greater than 5 mm, the planning target volume (PTV) will be expanded to account for respiration.

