#### 7.2.4 Nivolumab combined with Ipilimumab Dosing

Nivolumab combined with Ipilimumab will be dosed and scheduled according to FDA approved labels or per institutional guidelines at discretion of treating medical oncologist. For additional details regarding drug storage, preparation, and combination administration please refer to Nivolumab package insert[85]

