#### 15.2 Sample Size/Accrual Rate

The primary endpoint will be objective response rate at 16 weeks. The treatment regimen would be considered of insufficient activity for further study in this population if the 16 week objective response is 10% less than historical controls.

The objective response rate to CBI monotherapy depends on disease type and is reported to be approximately 40% in melanoma and 20-25% in NSCLC. Dual agent checkpoint blockade has recently been shown to have a response rate of 61% in Metastatic melanoma. In order to detect a cumulative relative 33% increase in objective response rate [i.e. from 61% to 81% (for dual agent), 40% to 53% for single agent in melanoma, and 25% to 33% in NSCLC] with a one tailed p value <0.05% with 80% power incorporating the respective frequencies of tumor types this would require 146 patients total.

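### The intended CBI regimen need not be declared before allocation, so the choice between one and two agents may be made with the arm known and may differ by arm.

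*Combined protocol and SAP*

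**What the plan says.** **Choice of regimen.** The synopsis states: "Commercially available checkpoint blockade immunotherapy will be administered intravenously as clinically indicated". Section 6.4 adds: "The patient will receive CBI as indicated and recommended by the treating medical oncologist". Sections 7.1.3 and 7.2.3 to 7.2.8 cover five single agents named under anti-PD-1/PD-L1 and ipilimumab. Section 7.2.4 also allows nivolumab with ipilimumab, to be dosed and scheduled by label or institutional guideline "at discretion of treating medical oncologist".

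**Timing.** Section 6.2 says that patients "should be enrolled and randomized prior to starting immunotherapy". It makes one exception: "patients who have started immunotherapy up to 5 days prior to enrollment will be still be eligible". The note to the schema repeats that window.

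**What is recorded at entry.** The synopsis makes a plan to give CBI an entry condition. Neither the inclusion list in 5.1 nor the checklist in 6.2 asks for the agent or the number of agents. For patients under 18, 5.1.9 requires a paediatric tumour board to agree to enrolment and to the potential use of CBI.

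**Masking and analysis.** The control is CBI alone. No sham or masking is described. The synopsis gives 1:1 allocation with no stratification factor, and 15.2 and 15.5 contain no adjustment for regimen.

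**Expected response.** Section 15.2 puts single-agent response at about 40% in melanoma and 20-25% in NSCLC. For two agents it says: "Dual agent checkpoint blockade has recently been shown to have a response rate of 61% in Metastatic melanoma".

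**The concern.** By the plan's own figures, the number of agents is closely tied to the primary endpoint. In melanoma the gap between one and two agents is 21 points, while the gain planned for SBRT is 13 points (single agent) or 20 points (dual agent).

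If an oncologist who knows the arm settles the regimen, the arms can differ in background treatment for reasons that randomisation does not control. Either direction is possible. An oncologist might hold back a second agent when SBRT is added: 15.3 notes the lack of published experience with the combination, and 4.2 mentions high-grade pneumonitis under anti-PD-1/PD-L1. That would count against SBRT. An excess of dual-agent use in the SBRT arm would count in its favour.

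This differs from chance imbalance, which the test's error rate already covers. Adjusting for the regimen received would not repair it either, because that regimen may itself depend on the arm.

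**Working it through.** **Inputs from the documents.** 73 per arm (synopsis). One-sided test; 15.2 prints the level as 0.05%, read here as 5%. Response 40% single-agent and 61% dual-agent in melanoma, 25% in NSCLC (15.2). Section 15.5 names no test, so a pooled z-test with all 73 per arm analysed is assumed.

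**Assumptions not in the documents.** Controls have 30% dual-agent use; the SBRT arm has 15 or 30 points more. The 40% and 61% are treated as the causal effect of regimen.

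**The plan's own figure.** For 61% versus 81%, one-sided 5%, 80% power, the pooled-variance formula gives 63 per arm, or 73 with continuity correction. That is 146 in total, which matches the plan. The match uses the dual-agent melanoma scenario alone; the tumour-type frequencies said to enter the calculation are not given.

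**Shift in response.** Shift = (61 − 40) × difference in dual-agent share, all patients with melanoma.

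| Difference in share | Shift in response | Against 13-point effect | Against 20-point effect |
|---|---|---|---|
| 10 points | 2.1 points | 16% | 11% |
| 20 points | 4.2 points | 32% | 21% |
| 30 points | 6.3 points | 48% | 32% |

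A shift of half the 13-point effect needs a difference of 6.5/21 = 31 points. Half the 20-point effect needs 10/21 = 48 points.

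**Type I error, no SBRT effect.** Let a and b be the control and SBRT response rates and p their mean. Then

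P(reject) = Φ{[(b − a) − 1.645 × √(2p(1 − p)/73)] / √([a(1 − a) + b(1 − b)]/73)}.

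*All melanoma.* a = 0.40 + 0.21 × 0.30 = 0.463.
- SBRT arm at 45% dual use: b = 0.4945, difference 3.15 points, error 10.3%.
- SBRT arm at 60% dual use: b = 0.526, difference 6.3 points, error 18.8%.

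*Half melanoma, the rest at 25% whatever the regimen.* a = 0.5 × 0.463 + 0.5 × 0.25 = 0.3565. The dual-agent shares now apply to the melanoma half.
- At 45%: b = 0.372, difference 1.6 points, error 7.4%.
- At 60%: b = 0.388, difference 3.15 points, error 10.5%.

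**Power, opposite direction, all melanoma.** SBRT response is held at 1.33 × 0.463 = 0.616. With no shift, power is 58%. With controls 15 or 30 points higher in dual-agent use, a = 0.4945 or 0.526 and power is 43% or 29%. The 58% starting point reflects the 46.3% control rate, not this concern; the plan states 80%.

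**Chance imbalance for comparison.** If half of an all-melanoma population receives two agents, the between-arm difference in share has SD √(2 × 0.25/73) = 8.3 points, or 21 × 0.083 = 1.7 points of response. The nominal 5% already allows for this.

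**The case against.** The strongest reply is that the documents never say the regimen is chosen after allocation. A reader might infer this from 6.2 and 6.4, but the text only permits it. A plan to give CBI precedes entry, patients within the 5-day window have already started a regimen, and under-18s need tumour-board agreement. Section 6.4 concerns duration, and the discretion in 7.2.4 concerns dosing and schedule, not the choice between one agent and two; the synopsis is the nearer source. This stands, and the point is worded accordingly. It does not close the gap, because a general plan to give CBI does not fix the number of agents.

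A second tempting reading is that regimen choice could account for a large part of the planned SBRT effect. The documents do not support it. Nearly half of the 13-point effect needs about a 30-point difference in dual-agent use, and nothing in the plan suggests one of that size. The only dual-agent rate is for melanoma, whereas 5.1.3 admits any histology. The 40% and 61% are separately reported rates, not a head-to-head contrast. A mixed population roughly halves the shift.

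Third, the schema figure is not shown. If it stratifies by CBI type, the regimen would have to be known before allocation and the point would be largely answered. The visible text gives no sign of this, but it cannot be excluded.

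**Conclusion.** The gap is real but modest. In the visible text the intended regimen need not be declared before allocation, patients are normally randomised before CBI starts, the choice is left to the oncologist, and no masking is described. Dual-agent use may therefore differ by arm and bias the response comparison in either direction.

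For a 15 to 30 point excess in the SBRT arm, one-sided type I error would be about 10-19% if all patients have melanoma, and about 7-11% if half do and the rest are unaffected by regimen. These figures rest on the assumed excess, the assumed 30% control share, and the use of the 40% and 61% rates as a regimen effect. They show sensitivity and do not predict what will happen. Nothing in the plan bounds the excess, and nothing shows that one will occur. This is a worthwhile low-cost improvement, not evidence that the comparison is invalid.

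**What to change.** In 6.2, require the intended CBI agent(s) to be entered on the randomisation form before the arm is released. For patients within the 5-day window, enter the regimen already started. The oncologist's choice of regimen stays as it is.

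Report by arm every starting regimen that differs from the declared one. In 15.5, add the declared (not the received) regimen as a baseline adjustment factor in the response comparison.

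The cost is one form field, a sentence in 6.2 and a little more analysis, with no change to the 146 patients. Declaration makes departures after allocation visible and discourages them, but does not remove bias from those that occur. Later changes on study, such as the step-down from combination therapy described in 8.2, also remain possible.

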#### 6.5 Duration of Follow-Up

It is anticipated that this study will last 5 years. Routine follow-up appointments as clinically indicated after 2 years will be used to capture and determine overall survival endpoints.

#### 6.6 Criteria for Patient Removal

Unacceptable adverse events grade IV or greater with an attribution of possibly related to CBI Monotherapy, Combination CBI, or CBI combined with SBRT.

Intercurrent illness that prevents further administration of treatment.

Extraordinary Medical Circumstance: If at any time the treating physician feels constraints of this protocol are detrimental to the patients's health the patient can be removed from protocol therapy.

Patient can elect to discontinue treatment at any time.

#### 6.7 Alternatives

The study has been designed to minimize potential risks to participants. This is primarily through designation of a dose range shown to be safe in previous SBRT trials and careful patient monitoring. The risks of CBI are detailed in section 7 as well as in the manufacturer treatment guidelines. Risks to confidentiality will be minimized by having access to study records available only to the investigators with the exception of the standard clinical records (lab values, dictations, operative notes, etc) which are maintained through the UCSD Health System and Moores Cancer Center.

Standard therapies for metastatic disease include conventional radiotherapy, chemotherapy, or observation. Such treatment may or may not be applicable for patients enrolled in this study. Regardless, patients will be expected to forgo standard chemotherapy or radiotherapy until there is evidence of clinical or radiographic disease progression. The amount of radiation administered via protocol therapy will be considered in determining how much additional radiation can be given using conventional external beam fractionation.

#### 6.8 Costs

Patients and/or their insurance companies will be responsible for the cost of all procedures and treatments under this protocol.

#### 6.9 Compensation

Patients and/or their insurance companies will be responsible for the cost of all procedures and treatments under this protocol.

#### 6.10 Withdrawal from Study

The reasons for withdrawal from the study include:

- Subject withdraws consent for follow-up.
- Subject is lost to follow-up.
- Study is terminated for any reason.

If participants withdraw from the study, they will be followed for survival data.

# 7. CHECKPOINT BLOCKADE IMMUNOTHERAPY DRUG INFORMATION

#### 7.1 ANTI-CTLA-4 DRUG INFORMATION AND ADMINISTRATION

#### 7.1.1 Relevant Prior Clinical Information

The results of a randomized, Phase 3 clinical trial published in 2010 showed a first-ever overall survival (OS) benefit for patients with previously treated stage III/stage IV metastatic melanoma who received ipilimumab compared with the controls. The patients in that trial (N=676) were randomized to receive either glycoprotein 100 (gp100) vaccine with Ipilimumab, gp100 alone, or Ipilimumab monotherapy in a 3:1:1 ratio. Patients receiving Ipilimumab monotherapy or with gp100 experienced a significantly longer median OS compared to those who received gp100 alone (approximately 10 vs. 6.4 months respectively). The risk of progression was reduced 19% with Ipilimumab plus gp100 and 36% with Ipilimumab alone compared to gp100 alone; subsequently, the FDA approved Ipilimumab alone in 2011. This OS advantage was observed while using a lower dose (3 mg/kg), than preceding studies (10 mg/kg) with a durable response demonstrated despite the lack of a maintenance phase.

In a Phase 1 trial testing ipilimumab in patients with stage III and IV melanoma, three doses were given: 0.3 mg/kg, 1 mg/kg, and 3 mg/kg. A dose-response was seen, with only the 3mg/kg dose achieving trough concentrations of 10 μg/mL. Steady state was achieved by the third dose at approximately 22 μg/mL. On average, the elimination half-life of Ipilimumab is 14.7 days. Volume of distribution and clearance increase with increasing body weight. The following mean (percent coefficient of variation) parameters have been generated through population pharmacokinetic analysis: terminal half-life of 15.4 days (34%); systemic clearance (CL) of 16.8 mL/h (38%) [17]. The volume of distribution at steady-state (Vss) is 7.21 L and the mean (±SD) Ipilimumab Cmin achieved at

steady state with the 3-mg/kg regimen is 21.8

The effects of various covariates on Ipilimumab pharmacokinetics have been assessed in population pharmacokinetic analyses. Ipilimumab CL increases with increasing body weight; however, no dose adjustment of ipilimumab is required for body weight after administration on a milligram per kilogram basis. The following factors have no clinically meaningful effect on the CL of Ipilimumab: age (range 26 to 86 years), gender, performance status, renal impairment, mild hepatic impairment, prior use of systemic anticancer therapy, or baseline lactate dehydrogenase (LDH) levels. [84].

Renal Impairment: Creatinine clearance at baseline does not have a clinically important effect on Ipilimumab pharmacokinetics in patients with calculated creatinine clearance values of 29 mL/min or greater [84].

Hepatic Impairment: Baseline AST, total bilirubin, and ALT levels does not have a clinically important effect on Ipilimumab pharmacokinetics in patients with various degrees of hepatic impairment [84].

#### 7.1.2 Safety Profile

Ipilimumab has been reported to cause high levels of adverse events (AEs), the most common of which are immune related[84]. Blockade of CTLA-4 may cause an increase in self-reactive T cells and autoimmunity leading to rash, vitiligo, diarrhea, colitis, uveitis, episcleritis, hepatitis and hypophysitis.called immune related adverse events (irAEs).

The results of dose escalation studies have shown that increasing dosage correlates with increased efficacy as well as increased severity of irAEs. Roughly 60% of patients taking Ipilimumab experienced an irAE of any grade, with 10-15% of those grade 3 or 4 at the 3mg/kg dose. The most commonly reported adverse effects at the 3 mg/kg dose are grade I and II adverse events including rash, pruritus and diarrhea[84]. A cases series of 11 patients found an increased rate of transaminitis compared to the results from the Hodi et al trial[37]. Six of eleven patients had >Grade 1 elevations of liver enzymes compared to only 3 patients in the Hodi trial; four of eleven had grade 3 elevations compared to none in the Hodi trial[37].

irAEs can have a delayed onset and may be persistent. The reported median time to onset of an irAE depends on event type but ranges from 3.1 to 11 weeks. The median time to resolution of any grade II-IV event has been reported to be 4.9 weeks. Diarrhea, the most common irAE in clinical trials, has a median time to resolution of 1-2 weeks but it may be longer than 4 weeks for a grade III or IV event. The standard of care for treating irAEs is systemic administration of corticosteroids, as the majority of irAEs caused by ipilimumab can be resolved with steroids alone. Additional therapies that have been published include immune-suppressants, hormone replacement therapy for irAEs of the endocrine system, and intravenous immunoglobulin for immune-mediated blood disorders.

Ipilimumab has been attributed to the death of 14 patients in the Hodi et al trial, 7 of those due to immune related adverse events[37]. A boxed warning regarding the risk of enterocolitis, hepatitis, dermatitis, neuropathies, and endocrinopathies is included with ipilimumab. A Risk Evaluation and Mitigation Strategy (REMS) program for ipilimumab is mandated by the FDA to ensure that the benefits of ipilimumab outweigh the risk of these severe irAEs.

#### 7.1.3 Ipilimumab Dosing

Ipilimumab will be dosed and scheduled according to FDA approved labels or per institutional guidelines at discretion of treating medical oncologist. For additional details regarding drug storage, preparation, and administration please refer to Ipilimumab package insert[84].

#### 7.1.4 Treatment of Ipilimumab Related Infusion Reactions

Infusion reactions should be graded according to CTCAE Version 4.0 Allergic reaction/hypersensitivity criteria. Severe infusion reactions require the immediate interruption of ipilimumab therapy and permanent discontinuation from further treatment. Appropriate medical therapy including epinephrine, corticosteroids, intravenous antihistamines, bronchodilators, and oxygen should be available for use in the treatment of such reactions. Subjects should be carefully observed until the complete resolution of all signs and symptoms. In each case of an infusion reaction, the investigator should institute treatment measures according to the best available medical practice.

#### 7.2 ANTI-PD-1/ ANTI-PD-L1 DRUG INFORMATION AND ADMINISTRATION

#### 7.2.1 Relevant Prior Clinical Information

Nivolumab (Opdivo) is a fully human monoclonal immunoglobulin (Ig) G4 antibody that binds to the programmed death-1 (PD-1) cell surface membrane receptor, a negative regulatory molecule expressed by activated T and B lymphocytes [85].

Inhibition of the interaction between PD-1 and its ligands promotes immune responses and antigen-specific T cell responses to both foreign antigens as well as self antigens. PD-1 receptor blockade by Nivolumab is an FDA approved approach for immunotherapy of advanced metastatic melanoma, lung cancer, and renal cell carcinoma[85]. Nivolumab received FDA approval on March 4th 2015 for treatment of advanced squamous NSCLC that has progressed after treatment with platinum-based chemotherapy. In the phase II clinical trial CheckMate-063, tumors shrank in 15% of patients who took Opdivo, and 26% had stable disease. Additionally the phase III CheckMate-017 trial in which NSCLC patients received either docetaxel chemotherapy or Opdivo was stopped early after it became evident that nivolumab outperformed docetaxel.

Pembrolizumab (Keytruda) is a human programmed death receptor-1 (PD-1)-blocking antibody and is an FDA approved approach for immunotherapy of advanced

metastatic melanoma and lung cancer [86]. Pembrolizumab received FDA approval on Oct  $2^{nd}$ , 2015 for advanced (metastatic) non-small cell lung cancer (NSCLC) whose disease has progressed after other treatments and with tumors that express PD-L1. The accelerated FDA approval was based on a multicenter, open-label multicohort, activity-estimating study (KEYNOTE-001), which evaluated Pembrolizumab in a cohort of 280 patients with metastatic NSCLC that had progressed following platinum-containing chemotherapy and any evidence of PD-L1 expression by a clinical trial immunohistochemistry assay. In the KEYNOTE-001 trial Keytruda resulted in an overall response rate of 41% (n=25/61) in patients who had PD-L1 positive tumors (Tumor proportion score  $\geq 50\%$ ).

Atezolizumab (Tecentriq) is a fully humanized, engineered monoclonal antibody of IgG1 isotype against the protein programmed cell death-ligand 1 (PD-L1). It has multiple FDA approved indications.

Avelumab (Bavencio) is a fully human monoclonal antibody targeting the protein programmed death-ligand 1 (PD-L1). It was FDA approved in March 2017 for Merkel-cell carcinoma.

Durvalumab (Imfinzi) is a human immunoglobulin G1 kappa ( $IgG1\kappa$ ) monoclonal antibody that blocks the interaction of programmed cell death ligand 1 (PD-L1). It has multiple FDA approved indications.

